8.2 Adverse Event Reporting

8.2.1 Adverse Event Reporting Period

After signing of the pre-screening informed consent, AEs due to the protocol-required intervention will be collected in the pre-screening phase.

After signing of the main study informed consent, all SAEs and AEs regardless of attribution will be collected until 30 days after the last dose of study drug or start of a new treatment of antitumor therapy, whichever is earlier. The relevant AEs will be followed up until they are recovered to the baseline status, already in a stable state as assessed by the investigator, start of new antitumor therapy, loss to follow-up, death, withdrawal of informed consent, the end of study, or it has been confirmed that the AEs are unrelated to the study drug. After this period, the investigators should report only SAEs that are considered to be related to the study drug.

8.2.2 Expedited Reporting

Certain events require immediate reporting to allow the Sponsor to take appropriate measures to address potential new risks in a clinical trial. The investigator must report such events (both initial and follow-up) to the Sponsor immediately; under no circumstances should reporting take place more than 24 hours after the investigator learns of the event. The following is a list of events that the investigator must report to the Sponsor within 24 hours after first learning of the event, regardless of relationship to study drug:

- SAEs
- Pregnancy

8.2.3 Dose Limiting Toxicity Reporting

For each DLT event that occurs in the dose escalation part, the investigator must confirm to the Sponsor within 2 business days after learning of it and should conduct phone or online meetings with the medical monitor and report any DLT events observed in the DLT evaluation window.

8.3 Prior and Concomitant Therapies

8.3.1 Prohibited Therapies

Any therapy intended for the treatment of cancer (with exceptions as noted in Section 8.3.2), whether currently marketed or experimental, is prohibited. This includes, but is not limited to, the following: chemotherapy, hormonal therapy, biologic therapy, radiotherapy, or herbal therapy.

Concomitant use of medications that have a known risk of causing QT prolongation and/or torsades de pointes (refer to [Appendix 5](#)).

HMPL-306 is a substrate of CCI [REDACTED]. The potential effects of medications that can affect the PK of HMPL-306 via CCI [REDACTED] pathway have not been tested in the clinic. During the study treatment period, medications that can CCI [REDACTED] ([Appendix 6](#)) should be avoided, and such drugs should be discontinued 1 week or 5 half-lives (whichever is longer) before the start of the study treatment.

Prophylactic use of antiemetic drugs or colony-stimulating factors, platelet irritation factor, or erythropoietin is not allowed during the DLT assessment window. Outside the DLT assessment window, it may be allowed if the investigator considers it necessary.

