E=increased to the next higher dose; D=reduced to a previous lower dose; DLT=dose-limiting toxicity; DU=reduced to a previous lower dose and the current dose will not be used again in this trial; MTD=maximum tolerated dose; mTPI-2=modified toxicity probability interval-2; pT=toxicity probability; S=maintaining the same dose.

*If 2 out of 2 subjects have DLTs when treated at the lowest dose level, the Sponsor, based on recommendations from the Safety Review Committee (SRC), can choose to terminate the study or to enroll 1 more subject.

Note: The horizontal axis indicates the number of subjects who are treated at the current dose, and the longitudinal axis is the number of subjects observed with DLTs. ϵ_1 and ϵ_2 are fractions used to define an equivalence interval of the MTD.

Safety Review Committee

Safety monitoring and evaluation of dose escalation will be carried out by the SRC, which is comprised of the Sponsor and investigators. The SRC will determine whether it is safe to continue to the next predefined dose level, stay at the currently assigned dose level, or whether the dose should be de-escalated to a lower dose level and finally determine the RP2D based on the risk-benefit evaluation.

Dose -Limiting Toxicity

DLT is defined as the occurrence of any of the treatment-emergent adverse events (TEAEs) described in Section 8.1.3 during the DLT assessment window, unless the TEAEs are clearly unrelated to the study drug or judged by the investigator as not clinically significant.

DLT Assessment Window:

For all subjects in dose escalation, DLTs will be assessed during the DLT assessment window of 28 days (Cycle 1 Day 1 [C1D1] through C1D28).

DLT-Evaluable Subject:

A subject is DLT evaluable if the following criteria are met:

- Has received at least 75% of the assigned dose of study medication during the DLT assessment window

OR

- Has not completed the DLT assessment period due to a DLT

For decisions on dose escalation, each dose cohort shall present protocol-required numbers of DLT-evaluable subjects. Subjects who are not DLT evaluable in a dose cohort will be replaced to guarantee the protocol-required numbers of DLT-evaluable subjects for dose escalation evaluations.

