8.1.3 Dose-Limiting Toxicity

DLT is defined as the occurrence of any of the following TEAEs during the DLT assessment window, unless the TEAEs are clearly unrelated to the study drug or judged by the investigator as not clinically significant.

1. Non-hematologic toxicities:
 - Any Grade 4 non-hematologic toxicity
 - Grade 3 non-hematologic toxicity, except for the following conditions:

- Recovered to Grade ≤ 1 within 3 days after supportive therapy is administered for nausea, vomiting, diarrhea, constipation, fatigue, and electrolyte imbalance
 - Grade 3 hypothyroidism, adrenal gland or pituitary insufficiency, and inflammatory reactions at the tumor site
 - Grade 3 hypertension downgraded to Grade ≤ 1 within 1 week with appropriate supportive therapy
2. Hematologic toxicity:
- Grade ≥ 3 febrile neutropenia (neutrophil count $< 1.0 \times 10^9/L$, accompanied with a single body temperature measurement of $\geq 38.3^\circ C$ or $\geq 38^\circ C$ persisting for 1 hour)
 - Grade 4 neutropenia
 - Grade 4 thrombocytopenia
 - Grade 3 thrombocytopenia accompanied with clinically significant bleeding, in addition to that requiring transfusion
 - Grade 4 anemia requiring a dose delay of ≥ 14 days
3. Any life-threatening complication or abnormality not covered in the NCI CTCAE Version 5.0.

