8.3.2 Permitted Therapies

Concomitant therapy includes any prescription medications or over-the-counter preparations used by a subject. All concomitant therapy within 28 days prior to randomization and the Safety Follow-up visit should be reported to the investigator and recorded on the appropriate eCRF.

Subjects who use oral contraceptives, hormone-replacement therapy, or other allowed maintenance therapy may continue their use if indicated.

Prophylactic antiemetic, granulocyte colony-stimulating factors, granulocyte macrophage colony-stimulating factors, platelet-simulating factors, or erythropoietin are permitted as clinically indicated.

Levetiracetam is the preferred agent for epileptic prophylaxis. Other agents may be used but require prior discussion with the Sponsor before initiation unless medically urgent.

All supportive measures consistent with optimal subject care will be given throughout the study.

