7. CHANGE FROM THE PROTOCOL

Here is a list of changes in this analysis plan compared with the protocol

- The DLT- evaluable analysis set definition in the protocol is to include all patients enrolled into dose escalation part of the study who (i) either received at least 75% of assigned doses of the HMPL-306 during the DLT assessment window (i.e. Cycle 1 Day 1 [C1D1] through C1D28) or (ii) experienced a DLT in Cycle 1. However, since these criteria have been incorporated in the SRC review, the DLT-evaluable analysis set will be based on the decision from the SRC review.
- Though there is no protocol amendment, it was noted that the study did not proceed to the dose expansion part. That is, no patients were enrolled to the expansion cohorts A (cholangiocarcinoma), B (skeletal chondrosarcoma), C (low-grade glioma), C-1 (perioperative glioma), and D (any other solid tumor harboring an IDH mutation). Hence, the analysis of the study will be conducted only for the dose escalation part.
- DLT-equivalent summary was defined in the protocol, consider that DLT-equivalent event was not well collected in EDC, this summary will not be done.

REFERENCE

Guo W, Wang S-J, Yang S, et al. A Bayesian interval dose-finding design addressing ckham's Razor: mTPI-2. *Contemp Clin Trials*. 2017;58:23-33.

van den Bent M, Wefel J, Schiff D, Taphoorn M, Jaeckle K, Junck L, Armstrong T, et al. Response assessment in neuro-oncology (a report of the RANO group): assessment of outcome in trials of diff use low-grade gliomas. *Lancet Oncol*. 2011;12:583-93.

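### Amendment 2 permits in Section 8.3.2, without time limit, the prophylaxis that Section 8.3.1 bars in the DLT window, and the 8.3.1 QT-drug sentence has no verb and cites the wrong appendix

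*Protocol*

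**What the plan says.** **Prophylaxis.** The last paragraph of Protocol Section 8.3.1 (Prohibited Therapies) says that prophylactic antiemetics, colony-stimulating factors, platelet factors or erythropoietin use "is not allowed during the DLT assessment window". Outside the window it leaves their use to the investigator. Section 8.3.2 (Permitted Therapies) names prophylactic antiemetics, G-CSF and GM-CSF and ends "platelet-simulating factors, or erythropoietin are permitted as clinically indicated". It mentions neither the window nor 8.3.1. The one written link between the two sections is in the first paragraph of 8.3.1, which bars anticancer therapy "with exceptions as noted in Section 8.3.2". That link concerns a different class of treatment, and it points towards 8.3.2 as the place for exceptions.

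**Evaluability.** Section 4.1.1 makes a subject DLT-evaluable if the subject "Has received at least 75% of the assigned dose of study medication during the DLT assessment window", or failed to complete the window because of a DLT. SAP Section 7 says "the DLT-evaluable analysis set will be based on the decision from the SRC review".

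**QT drugs.** The 8.3.1 text is "Concomitant use of medications that have a known risk of causing QT prolongation and/or torsades de pointes", followed by a reference to Appendix 5 and a full stop. Appendix 5 is the NYHA functional classification. The QT drug list is Table 12 in Appendix 4, which is titled Prohibited Medications.

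**The concern.** Part 1 exists to find the MTD and/or RP2D, and Table 6 turns DLT counts into dose decisions. Section 8.1.3 already allows for reactive treatment: some Grade 3 events are not DLTs if they recover to Grade 1 or lower "within 3 days after supportive therapy is administered for nausea, vomiting, diarrhea, constipation, fatigue, and electrolyte imbalance". Prophylaxis works differently, because it can stop the event from being seen at all. That is the reason for a ban in the window, and a permission on the next page without the same limit undercuts it. Events open to this include Grade 3 vomiting that would not have recovered in 3 days and, in principle, Grade 4 neutropenia.

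The QT defect concerns safety, not the DLT count. Table 3 names QTcF prolongation as a class effect of IDH inhibitors. The on-treatment drug rule is one layer of protection, and as written it sends the site to a page with no drugs on it.

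**Working it through.** The plan gives no figure on this point, so there is none to reproduce. The check sets the texts side by side and then reads Table 6.

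**1. Do the sections conflict?**

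| | 8.3.1 | 8.3.2 |
|---|---|---|
| Classes | antiemetics, CSFs, platelet factors, erythropoietin | the same |
| Use | prophylactic | prophylactic |
| Days 1 to 28 of Cycle 1 | barred | permitted if clinically indicated |
| Later | investigator's judgement | permitted if clinically indicated |
| Reference to the other section on this point | none | none |

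The rows agree except inside the DLT window, where they contradict each other. These sentences are in the body text, not in a change log, and no redaction falls in them.

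**2. Does the evaluability rule close the gap?** No. A subject who took prophylaxis, took at least 75% of the dose and had no DLT meets the written rule. Removing that subject would need a judgement by the SRC, for which neither document gives a criterion on prophylaxis.

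**3. What can one masked DLT do in Table 6?**

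| n at the dose | Count without masking | Count with one DLT masked |
|---|---|---|
| 3 | 1 = D | 0 = E |
| 4, 5 | 1 = S | 0 = E |
| 6 | 2 = D | 1 = E |
| 7 to 10 | 2 = S | 1 = E |
| 11, 12 | 3 = S | 2 = E |

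Any decision table has such tipping counts. What matters here is that at n = 3, the minimum cohort, a single event separates escalation from de-escalation.

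**4. Illustration of size.** Let p be the true DLT rate and m the share of DLTs prevented across a cohort. Both are assumptions; neither is in the documents. The observed rate is q = p(1 − m). Then

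- P(E at n = 3) = (1 − q)³
- P(E at n = 6) = (1 − q)⁶ + 6q(1 − q)⁵

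| p | m | q | P(E), n = 3 | P(E), n = 6 |
|---|---|---|---|---|
| 0.40 | 0 | 0.40 | 21.6% | 23.3% |
| 0.40 | 0.10 | 0.36 | 26.2% | 30.1% |
| 0.40 | 0.25 | 0.30 | 34.3% | 42.0% |
| 0.40 | 0.50 | 0.20 | 51.2% | 65.5% |
| 0.25 | 0 | 0.25 | 42.2% | not computed |
| 0.25 | 0.10 | 0.225 | 46.5% | not computed |
| 0.25 | 0.25 | 0.1875 | 53.6% | not computed |
| 0.25 | 0.50 | 0.125 | 67.0% | not computed |

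The row m = 0 is the case in which every site follows 8.3.1. A rate of 0.40 lies above the 20% to 30% equivalence interval; 0.25 is the target. The n = 6 column treats six subjects as enrolled before any decision. In practice Table 6 has no S at n = 3, so reaching six at a dose depends on earlier results, and the unconditional binomial is only a rough guide.

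**5. Exposure.** In Amendment 2 the levels still to be run are 5 to 8, with at least 3 subjects each. If all four open, that is 4 × 3 = 12 subjects at minimum.

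**6. QT reference.** Exclusion 11 cites Appendix 4 for QT-prolonging drugs, and exclusion 5 cites Appendix 5 for NYHA class. Both match the appendices, so the reference in 8.3.1 is the wrong one. How many subjects it could affect cannot be derived.

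**The case against.** The strongest reply is that 8.3.1 states the window rule in full, for inside and outside, and a specific rule governs a general permission. On that reading only a cross-reference is missing. This is right about intent, but the protocol does not say which section prevails, and a site that opens Permitted Therapies finds an unqualified yes.

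Second, masking would not be invisible. Concomitant drugs go into the eCRF, the SAP lists them by patient and lists all protocol deviations, and the SRC sees the safety data and makes the dose decision. This stands. A reader might infer that a masked subject is bound to count as DLT-free; the documents do not support that, because the SAP leaves the evaluable set to SRC review.

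Third, few DLTs may be preventable. Table 3 lists no neutropenia risk; it lists leukocytosis with raised neutrophils. Entry requires an ANC of at least 1.5 × 10⁹/L, and quickly recovering Grade 3 vomiting is already exempt. This makes the larger assumed shares hard to credit and the antiemetic route more plausible than the G-CSF route.

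Fourth, on QT, a reader might infer that the strength of the rule is open, since 8.3.1 says of another drug group that it "should be avoided, and such drugs should be discontinued 1 week or 5 half-lives". The documents do not support that. The fragment stands under Prohibited Therapies, and the list is in an appendix titled Prohibited Medications. Other safeguards also remain: exclusions 10 and 11, Table 9 (hold drug, review QT-prolonging concomitant medication), triplicate ECGs at C1D1 and C2D1 with later ECGs, and central ECG analysis. Nor does the antiemetic permission in 8.3.2 lift the prohibition on a listed agent such as ondansetron.

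Fifth, the SAP is based on Amendment 3, which was not available. The point is therefore confined to Amendment 2.

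**Conclusion.** Both defects are present in Amendment 2, and both sit in rules that sites act on. The prophylaxis texts contradict each other inside the DLT window, and the written evaluability rule does not resolve it. The QT sentence is incomplete and points to the wrong appendix, although its intent is clear.

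Severity is minor to moderate. One masked DLT can turn D or S into E, but the documents do not say how often a site would follow 8.3.2 or what share of DLTs prophylaxis would prevent, so the escalation probabilities illustrate and do not estimate.

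Two stronger readings should be set aside. A reader might infer that past dose decisions were distorted. Section 4.1.1 reports no DLTs or safety concerns at levels 1 to 4, and nothing shows that prophylaxis was given or that any decision was affected. A reader might also take 12 subjects as a firm lower bound on exposure. It holds only if all of levels 5 to 8 open, and escalation runs only until the MTD or RP2D is reached.

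**What to change.** First check whether Amendment 3 already corrects the text. If it does not:

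- **8.3.2:** begin the prophylaxis sentence with *Outside the DLT assessment window (see Section 8.3.1), and subject to Appendix 4,*.
- **8.3.1:** complete the QT sentence with *is prohibited during study treatment (refer to Appendix 4)*.

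The cost is the wording of two sentences, carried in an amendment that Section 10.2 requires the IEC/IRB to review and approve. It needs no new data and no change to the analysis. If escalation has already finished, the by-patient concomitant-medication listing in SAP Section 5.2.7 can be used to see whether any of these drugs were given in Cycle 1.

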8.3.2 Permitted Therapies

Concomitant therapy includes any prescription medications or over-the-counter preparations used by a subject. All concomitant therapy within 28 days prior to randomization and the Safety Follow-up visit should be reported to the investigator and recorded on the appropriate eCRF.

Subjects who use oral contraceptives, hormone-replacement therapy, or other allowed maintenance therapy may continue their use if indicated.

Prophylactic antiemetic, granulocyte colony-stimulating factors, granulocyte macrophage colony-stimulating factors, platelet-simulating factors, or erythropoietin are permitted as clinically indicated.

Levetiracetam is the preferred agent for epileptic prophylaxis. Other agents may be used but require prior discussion with the Sponsor before initiation unless medically urgent.

All supportive measures consistent with optimal subject care will be given throughout the study.

8.3.3 Drug-Drug Interactions

There are currently no data on a drug demonstrating clear interactions with HMPL-306 in the human body. In vitro data indicate that HMPL-306 exhibited an CCI [REDACTED]

[REDACTED]

CCI

During the study treatment period, the use of medications that are CCI (Appendix 7) should be avoided. If the investigator believes it is necessary to use it, consent of the Sponsor-appointed medical monitor should be obtained before use, and close observation should be performed during use for a possible reduction in efficacy or increase in toxicity due to drug interactions.

8.3.4 Rescue Therapies

Not applicable.

8.3.5 Duration of Follow-up for Adverse Events

The investigator will follow all unresolved AEs and SAEs until the events are resolved or stabilized, the subject is lost to follow-up, subject's death, or the end of the study. Resolution of AEs and SAEs (with dates) should be documented on the appropriate eCRF and in the subject's medical record to facilitate source data verification (SDV). For SAEs, if, after follow-up, return to baseline status or stabilization cannot be established, an explanation should be recorded in the additional case details section of the eCRF.

For some SAEs, additional case details deemed necessary to appropriately evaluate the SAE report (eg, hospital discharge summary, consultant report, or autopsy report) may be followed-up by telephone, fax, email, and/or a monitoring visit.

All pregnancies that occur during the study should be followed until pregnancy outcome.

8.4 Eliciting Adverse Events

A consistent methodology of non-directive questioning for eliciting AEs at all subject evaluation time points should be adopted. Examples of non-directive questions include the following:

- “How have you felt since your last clinic visit?”
- “Have you had any new or changed health problems since you were last here?”

8.5 Assessment of Severity

Investigators will seek information on AEs and SAEs at each subject contact. All AEs and SAEs, whether reported by the subject or noted by authorized study personnel, will be recorded in the subject's medical record and on the appropriate AE/SAE form.

For each AE and SAE recorded on the applicable eCRF, the investigator will make an assessment of severity through clinical description by referring to the 5-grade determination standard in the NCI CTCAE Version 5.0. Please use the guideline below for the assessment of severity when the observed or reported AE is not listed in the NCI CTCAE Version 5.0:

- Grade 1: Mild; asymptomatic or mild symptoms; clinical or diagnostic observations only; intervention not indicated
- Grade 2: Moderate; minimal, local, or noninvasive intervention indicated; limiting age-appropriate instrumental activities of daily living (ADLs). (Note: Instrumental ADLs

refer to preparing meals, shopping for groceries or clothes, using the telephone, managing money, etc.)

- Grade 3: Severe or medically significant but not immediately life threatening; hospitalization or prolongation of hospitalization indicated; disabling; limiting self-care ADLs (Note: Self-care ADLs refer to bathing, dressing and undressing, feeding self, using the toilet, taking medications, and not bedridden).
- Grade 4: Life-threatening consequences; urgent intervention indicated
- Grade 5: Death related to AE

8.6 Causality Assessment

Investigators should use their knowledge of the subject, the circumstances surrounding the AE, and an evaluation of any potential alternative causes to determine whether an AE is considered to be related to the study drug. To ensure consistency of causality assessments, investigators should apply the general guidelines as provided in [Table 11](#) below:

Table 11 Determination of Correlation Between Adverse Events and Study Drug

Correlation	Criteria for Assessment
Not related	If there is no possibility of correlation between the event and the study drug, the adverse event will be deemed “unrelated” to the study drug. The situations that meet this assessment factor include, but are not limited to, the following: Adverse events caused by influence of underlying disease or concurrent disease or other drugs, unreasonable or no temporal relationship between the adverse events and the trial drug, and/or existence of other factors that may more likely lead to adverse events.
Related	If the event has a potential relationship with the study drug, the adverse event will be considered as “related” to the study drug. The situations that meet this assessment factor include, but are not limited to, the following: There is a reasonable temporal relationship between the adverse event and the study drug or the adverse event recurs after re-challenge; compared to the potential relationship with the study drug, the possibility of other factors that may cause the adverse event are not present, or the possibility is lesser or the same.

Ambiguous cases should be considered as being a “reasonable possibility” of a causal relationship unless further evidence becomes available to refute this. Causal relationship in cases where the disease under study has deteriorated due to lack of effect should be classified as no reasonable possibility.

